Primary outcome 1C1: Clinician-rated anxiety severity: Change in score on the Hamilton Anxiety Rating Scale (HAM-A) from initial assessment to one-month follow-up.

Primary outcome 1C2: Self-reported cognitive reappraisal use. Change in score on the reappraisal subscale of the Emotion Regulation Questionnaire (ERQ) from initial assessment to one-month follow-up.

Hypothesis 1C1: The veritable-NF group will report decreased symptom severity and increased CR use compared to the sham-NF group.

Hypothesis 1C2: Increase in NF-induced brain activation will correlate with decreased symptom severity and increased CR use at follow-up.

3. Background Information

Burden of anxiety disorders. Anxiety disorders are the most common mental health condition worldwide and a leading cause of disability,² associated with increased risk for suicide³ and chronic health problems⁴. Over the lifespan, prevalence rates of anxiety increase most dramatically during young adulthood (age 18-24)⁵, pointing to a critical developmental period for prevention and treatment. Moreover, heterotypic continuity of anxiety disorders is observed from adolescence to young adulthood suggesting common underlying mechanisms⁶. Although cognitive behavioral therapy (CBT) is regarded as a gold-standard treatment for anxiety, associated with moderate effect sizes in meta-analyses^{7,8}, remission rates are low⁹ and relapse is common,^{10,11} resulting in an unmet need to improve beyond existing evidence-based treatments.

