4.3.2 Study Visit 1: Informed Consent, Diagnostic Interview

Informed Consent. The informed consent form will be mailed in advance of the visit. During this first study visit, participants will be given detailed information about the study. During this meeting, the potential subject will be encouraged to ask questions about the study, after which the informed consent form will be reviewed and signed. Study staff will go through and explain the informed consent document to the participant, which will be available and visible on SignNow. After the participant digitally signs the document, the research assistant will sign the document.

Diagnostic Interview and Questionnaires. Consented participants will then undergo a diagnostic interview, including the clinician-administered SCID-5 and CGI (see Section 4.5.1). This diagnostic assessment will be used to make the final determination about study eligibility. Participants will also be given the HAM-A to assess baseline anxiety severity in the past week. This visit may take 1-3 hours in total, depending on how many symptoms a subject endorses.

Randomization. Participants who meet eligibility criteria following the diagnostic interview will be invited to schedule Study Visits 2 and 3. Study Visit 2 will occur 1-5 days before Study Visit 3. In arms 2 and 3, a designated member of the study staff who will remain *unblinded* during the duration of the study will randomly assign participants to one of the two groups (veritable-NF or sham-NF). Approximately one-half of the sample will be assigned to each group. All staff interacting with the participant, including the participant themselves, will be *blinded* to group assignment. To this end, the unblinded staff member will code the MRI scanning sequences with sets of random numbers that will be used to communicate to the MRI Technician which neurofeedback protocol should be employed during each study visit without revealing visually or by name if true feedback is being generated.

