4.3.3 Study Visit 2: Reappraisal Practice

Cognitive Reappraisal Practice Training. During Study Visit 2, participants will first complete a series of self-report questionnaires assessing mental health symptoms and use of emotion regulation strategies (see Section 4.5.1). Next, participants will complete a 30–45-minute practice session with a member of the study staff. Negative images, like those that will be shown during the MRI session, will be displayed via Zoom if the visit is remote or displayed using the mock scanner if the visit is in-person. Participants will be guided to reinterpret situations to reduce negative affect ('reappraise' trials). During 'look' trials, participants will be instructed to passively view a picture as they normally would without trying to alter the emotional response. Research staff will be recording participants responses and performance on the pre-fMRI Scan Image Questions survey in REDCap. This visit may take up to an hour.

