To assess group differences in CR ability (**hypothesis 1B1**), a repeated-measures LME with participant as a random intercept, will examine the interaction of group (veritable-NF, sham-NF) x condition time (baseline, NF1, NF2, NF3, transfer) on negative affect ratings and prefrontal-amamygdala connectivity during the ERT. We will use a psychophysiological interaction analysis to measure prefrontal-amamygdala connectivity. Deconvolved time series from anatomical bilateral amygdala seeds for each participant will be multiplied by a vector for the reappraise > look contrast at each run. Regressors for the seed time series, the original condition and the interaction term will be convolved with the canonical hemodynamic response function. Contrast maps will be entered into second-level random effects analyses to test if veritable-NF shows greater prefrontal-amamygdala connectivity than sham-NF.

For hypothesis 1B2, linear regressions will examine run-by-run associations between dm/vlPFC activity and 1) negative affect ratings and 2) prefrontal-amamygdala connectivity, across all participants irrespective of training condition.

Aim 1C. Assess the impact of NF on anxiety symptoms and CR use over time (exploratory).

To examine the effect of NF on anxiety (**hypothesis 1C1**), a repeated-measures LME with participant as a random intercept, will examine the effect of time (baseline, 1 month) x group (veritable-NF, sham-NF) on the HAM-A. To examine the effect of NF on CR use (**hypothesis 1C1**), a repeated-measures LME with participant as a random intercept will examine the interaction of time (baseline, 2-week, 1-month) x group (veritable-NF, sham-NF) on the ERQ.

Linear regressions will examine the association between dm/vlPFC change (transfer-baseline) and change in HAM-A and ERQ scores (1 month – baseline) across all participants (**hypothesis 1C2**). Exploratory: Mediation will test if change in dm/vlPFC activity mediates the relationship between NF group and change in HAM-A or ERQ scores.

7. Data and Safety Monitoring Plan

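### Exploratory Aim 1C: with complete data the planned HAM-A model compares mean change between arms; adjusting for baseline HAM-A is usually more precise and costs very little

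*Combined protocol and SAP*

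**What the plan says.** Section 2 lists HAM-A as primary outcome 1C1, under an aim labelled exploratory, and defines it as "Change in score on the Hamilton Anxiety Rating Scale (HAM-A) from initial assessment to one-month follow-up". Section 6, Aim 1C, analyses it with a repeated-measures linear mixed model with a participant random intercept, which "will examine the effect of time (baseline, 1 month) x group (veritable-NF, sham-NF) on the HAM-A". It names no baseline covariate and does not constrain the arms to a common baseline mean. Section 6 then adds an exploratory mediation analysis of the arm effect on change in HAM-A.

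Baseline HAM-A comes from Visit 1. Section 4.3.2 states: "Participants will also be given the HAM-A to assess baseline anxiety severity in the past week". Assignment comes later. The same section says "Participants who meet eligibility criteria following the diagnostic interview will be invited to schedule Study Visits 2 and 3" and then describes random assignment, while the schedule in Section 4.5 puts randomization at Visit 2. On either reading the baseline HAM-A comes before assignment.

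**The concern.** In a two-arm randomized comparison with one baseline and one follow-up measurement, the baseline can be subtracted in full or used as a covariate with an estimated slope. Both are unbiased under randomization. Subtracting in full also subtracts baseline noise that does not carry over to follow-up, and this usually widens the interval. At stake is the width of the confidence interval for the HAM-A arm difference. For an exploratory aim with no stated power, that interval is the main thing the analysis will deliver.

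**Working it through.** **Inputs from the documents.** Two HAM-A visits, a participant random intercept and a time x group term (Section 6); about half the sample in each arm and baseline HAM-A at Visit 1 (Section 4.3.2). The documents state no sample size, power, HAM-A SD, dropout rate or correlation, so there is no figure of the plan's own to reproduce. Everything below on rho, SDs, total N and dropout is assumed and shown as a range.

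**Step 1: what the planned model estimates.** Let B and F be an arm's mean HAM-A at baseline and one month. With both main effects in the model and complete data, the interaction is

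(F_ver − F_sham) − 1 × (B_ver − B_sham).

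Check on simulated data, 20 per arm, rho = 0.3: the REML random-intercept interaction was −2.637 (SE 1.690). Regression of the change score on arm gave the same estimate and SE.

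**Step 2: what adjustment does.** ANCOVA replaces the 1 by b, the within-arm slope of one-month on baseline HAM-A. With SDs s0 (baseline) and s1 (one month), and up to a common factor, the variances are:

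- change: s0² + s1² − 2·rho·s0·s1
- ANCOVA: s1²·(1 − rho²)

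With k = s0/s1, the large-sample ratio ANCOVA/change is (1 − rho²)/(k² + 1 − 2·rho·k).

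- Equal SDs (k = 1): this reduces to (1 + rho)/2, giving 0.65, 0.75, 0.85 and 0.95 at rho 0.3, 0.5, 0.7 and 0.9.
- rho = 0.5: k = 1.2 gives 0.75/1.24 = 0.60; k = 0.8 gives 0.75/0.84 = 0.89; k = 0.7 gives 0.75/0.79 = 0.95.
- k = rho: the denominator becomes 1 − rho², so the ratio is 1 and there is no gain.

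**Step 3: small samples.** Estimating b multiplies the ANCOVA variance by 1 + 1/(N − 4), that is 1/16 = 6%, 1/26 = 4% and 1/56 = 2% at total N of 20, 30 and 60. With equal SDs, adjustment still gains while rho is below (N − 5)/(N − 3): 15/17 = 0.88, 25/27 = 0.93 and 55/57 = 0.96.

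Simulated 95% interval widths, ANCOVA/change, t-based, total N = 30, 20,000 runs per setting:

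| k | rho 0.3 | rho 0.5 | rho 0.7 | rho 0.9 |
|---|---|---|---|---|
| 1.2 | 0.74 | 0.79 | 0.84 | 0.84 |
| 1.0 | 0.82 | 0.88 | 0.94 | 0.99 |
| 0.8 | 0.90 | 0.96 | 1.01 | 0.99 |
| 0.7 | 0.94 | 0.99 | 1.02 | 0.93 |

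The least favourable setting tried, k = rho = 0.7, is 3% wider at N = 20, 2% at N = 30 and 1% at N = 60. Across all 48 settings coverage was 94.6 to 95.3% for both methods, so the narrowing is not undercoverage.

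**Step 4: dropout.** The planned model also uses participants who have only a baseline score; ANCOVA does not. With equal SDs and a proportion p followed up, the large-sample ratio is (1 + rho)/((1 + rho) + p·(1 − rho)). At rho = 0.5:

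- p = 1: 1.5/2.0 = 0.75
- p = 0.85: 1.5/1.925 = 0.78
- p = 0.70: 1.5/1.85 = 0.81

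**The case against.** The strongest reply is that this is preference. The outcome is defined as change, the planned interaction estimates change without bias, the aim is exploratory, and every magnitude above is assumed. Much of that stands. No planned conclusion becomes wrong, and nobody can say from the documents how large the gain would be in this trial. The 26% narrowing in the table is its most favourable cell, not a forecast. In a single dataset the adjusted SE can even be slightly larger: at rho = 0.5 with 20 per arm, one simulated example gave 1.614 against 1.609.

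Dropout also counts against the gain. In a simulation at N = 30 and rho = 0.5 that treated rho as known in the planned model, which slightly favours that model, the variance ratio was 0.78, 0.83 and 0.87 at 100%, 85% and 70% follow-up. At rho = 0.9 it was 1.00, 1.01 and 1.02.

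Coherence is a fair point too. With complete data, the planned 1C1 contrast equals the total effect in the mediation analysis. Adjusting only the first would make the two disagree.

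What does not stand is the conclusion that the point should be ignored. The covariate is already collected, the change endpoint is kept, and the trade is lopsided: a plausible gain against a loss of at most a few percent.

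**Conclusion.** The point holds as an optional efficiency gain of the lowest severity, for HAM-A only. Its size depends on assumed correlation, SD ratio, sample size and follow-up, and it can be nil or slightly negative.

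Two stronger readings are tempting, and the documents support neither. A reader might infer that the planned HAM-A analysis is biased or invalid. It is not: arms are assigned at random and the interaction estimates the outcome that Section 2 defines. A reader might also infer that the ERQ model needs the same treatment. That model has three visits, so the identity with mean change carries over only to the one-month estimate, not to its standard error or to the joint interaction test. Whether its covariance assumption matters depends on correlations that the documents do not give. That is a separate, conditional question and no part of this point.

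**What to change.** In Section 6, Aim 1C, state that the one-month HAM-A arm difference will be estimated by ANCOVA on arm and baseline (Visit 1) HAM-A, with t-based inference. The outcome may be the one-month score or the change score. The arm coefficient is the same, because subtracting baseline from the outcome only lowers the baseline slope by 1, so the Section 2 endpoint is untouched. Include baseline HAM-A in the mediator and outcome equations of the HAM-A mediation analysis as well, so that its total effect matches the reported arm difference in the same participants.

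The cost is one rewritten HAM-A model sentence, one added covariate in the mediation analysis and one degree of freedom, with a small loss of precision in unfavourable cases. No new data or visits are needed. Fixing the covariate in the plan also avoids choosing it after the results are seen.

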Neurofeedback Enhanced Cognitive Reappraisal Training

Principal Investigator (PI): [name] [name]

University of Michigan

Dept of Psychiatry

[name]

Email: [contact]

Co-Investigator(s):

[name], [name], [name], [name], [name], [name], [name]

Sponsor:

Brain & Behavior Research Foundation

HUM Number:

HUM00209563

NCT Number:

NCT06132659

Version:

3.21.2025

DETAILED IRB PROTOCOL**1. Objective**

Anxiety disorders are the most common mental health condition worldwide and a leading cause of disability. The development of novel interventions to treat anxiety has lagged the advancements made regarding the neurobiology of emotion and cognitive processes directly related to treatment. This proposal will utilize real-time functional magnetic resonance imaging neurofeedback (NF) to modulate key brain regions involved in emotion regulation to enhance effectiveness of cognitive reappraisal, a central skill taught in evidenced-based psychotherapies. This innovative project will identify 1) the ability of adults with anxiety to self-modulate brain function in regions specific to healthy emotion regulation using NF and 2) the potential impact of neuromodulation on improved emotion regulation ability and anxiety reduction.

2. Specific Aims/Hypotheses

Aim 1A. Evaluate the ability of adults with anxiety to increase prefrontal cortex activity during CR based on NF.

Primary outcome 1A: BOLD activation. Change in PFC activity (baseline to transfer run) from the reappraise > look contrast.

Hypothesis 1A: Participants receiving veritable-NF will show a greater activation increase in the PFC compared to sham-NF.

Aim 1B. Determine the relationship between prefrontal cortex activity recruitment and CR ability in adults with anxiety.

Primary outcome 1B: Negative affect ratings. Decrease in negative affect ratings (baseline to transfer run) from reappraise > look contrast.

Secondary outcome 1B: Prefrontal-amamygdala connectivity. Change in amygdala-PFC functional connectivity (baseline to transfer) from reappraise > look contrast.

Hypothesis 1B1: Participants receiving veritable-NF will show greater CR ability compared to those receiving sham-NF.

Hypothesis 1B2: prefrontal cortex activation will positively correlate with CR ability.

Aim 1C. Assess the impact of NF on anxiety symptoms and CR use over time (exploratory).

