Real-time fMRI neurofeedback. Despite advances made in our understanding of the brain, translation of knowledge from functional magnetic resonance imaging (fMRI) research into clinical practice has been²⁷, possibly stemming from the correlational nature of fMRI design, and the reliance of fMRI inferences on group averages. To make fMRI clinically applicable, reliable, and valid methods are needed at the level of the individual patient. Real-time fMRI neurofeedback (NF) is a tool that has the potential to translate neuroimaging research to clinical practice. In this technique, participants see feedback based on their own neural signal as they engage in different psychological processes, which provides them an opportunity to become aware of and self-regulate their own brain signals²⁸. As such, NF can test causal relationships about brain and behavior²⁹ and can teach individuals a self-regulatory skill that could then be applied in real life. The field has cohered around practice standards³⁰ and two recent meta-analyses^{31,32} evaluating NF efficacy across psychiatric conditions reported medium-large effects sizes for neural activity and anxiety symptoms.. Thus, NF could be used to directly target vIPFC and dmPFC activity, potentially enhancing CR efficacy and use in adults with anxiety.

[figure not shown]

Figure 2. Illustration of NF³⁰

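### The PFC-outcome regressions for H1C2 and H1B2 pool the arms with no group term, so the pooled slope partly restates the arm comparison; an arm-adjusted slope should be reported beside it

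*Combined protocol and SAP*

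**What the plan says.** Section 6, Aim 1C, tests H1C2 by simple regression: "Linear regressions will examine the association between dm/vlPFC change (transfer-baseline) and change in HAM-A and ERQ scores". The outcome and analysis set are given as "change in HAM-A and ERQ scores (1 month – baseline) across all participants". No group term, group-by-PFC interaction or within-arm analysis is named. For H1B2, Section 6 (Aim 1B) relates dm/vlPFC activity, run by run, to negative affect ratings and to connectivity with the amygdala, "across all participants irrespective of training condition".

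Section 2 words H1C2 as a correlation: "Increase in NF-induced brain activation will correlate with decreased symptom severity and increased CR use at follow-up". The same section predicts an effect of arm on the predictor (H1A: "Participants receiving veritable-NF will show a greater activation increase in the PFC compared to sham-NF"), on CR ability (H1B1), and on symptoms and CR use (H1C1: "The veritable-NF group will report decreased symptom severity and increased CR use compared to the sham-NF group").

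Directly after the H1C2 regressions, Section 6 adds an exploratory mediation analysis from NF group through PFC change to change in HAM-A or ERQ. It gives no equations or covariates.

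**The concern.** Arm is, on the plan's own hypotheses, a common cause of the predictor and the outcome in these regressions. Leaving it out lets the difference between arm means enter the slope. If veritable feedback raises PFC activity and, by some other route, also lowers HAM-A or raises ERQ, the pooled data show an association in the hypothesised direction although PFC change says nothing about outcome among people in the same arm. That result looks the same as a true link between PFC change and outcome.

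This matters because Section 3 criticises earlier work for not tying change in brain function to change in behaviour, and these regressions are the named tests of that tie. When H1A and H1C1 both succeed, the pooled test of H1C2 partly counts the same evidence again.

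**Working it through.** **Plan's own figure.** There is none to reproduce: the documents state no sample size, power, significance level or expected correlation for these regressions.

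**Inputs from the documents.** Allocation is about 1:1 (Section 4.3.2: "Approximately one-half of the sample will be assigned to each group"). Arm effects on both variables are predicted (H1A, H1C1) without a size. The only guide is Section 3, which cites meta-analyses reporting "medium-large effects sizes for neural activity and anxiety symptoms".

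**Assumed.** Arm differences dx (PFC change) and dy (HAM-A or ERQ change, in the direction of benefit), in within-arm SD units; total N of 40 and 60; two-sided 5% test; within-arm correlation exactly zero.

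**Formula.** With equal arms, the between-arm covariance is dx·dy/4 and the total variances are 1 + dx²/4 and 1 + dy²/4, so

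r = (dx·dy/4) / √[(1 + dx²/4)(1 + dy²/4)].

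- 0.3/0.3: 0.0225/1.0225 = 0.02
- 0.5/0.5: 0.0625/1.0625 = 0.06
- 0.8/0.5: 0.10/√(1.16 × 1.0625) = 0.10/1.110 = 0.09
- 0.8/0.8: 0.16/1.16 = 0.14
- 1.0/0.8: 0.20/√(1.25 × 1.16) = 0.20/1.204 = 0.17
- 0.8/0: the numerator is 0, so r = 0

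The last line shows that an arm effect on both variables is needed.

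**Rejection rates for the H1C2 slope**, from 20,000 simulated trials per setting (repeat runs differ by up to about one percentage point):

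| dx / dy | induced r | N=40, no group term | N=60, no group term |
|---|---|---|---|
| 0.3 / 0.3 | 0.02 | 5% | 5% |
| 0.5 / 0.5 | 0.06 | 6% | 7% |
| 0.8 / 0.5 | 0.09 | 8-9% | 10% |
| 0.8 / 0.8 | 0.14 | 14% | 18-19% |
| 1.0 / 0.8 | 0.17 | 18% | 24-25% |

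With a group term, the rate stayed between 4.6% and 5.4% in every setting tried. Without it, the rate grows with N: 0.8/0.8 at N=100 gives 28%.

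**Hand check of one cell.** For 0.8/0.8 at N=60, Fisher's z is atanh(0.138) × √57 = 0.139 × 7.55 = 1.05. The chance of exceeding 1.96 is P(Z > 0.91), about 18%, which agrees.

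**What the formula does not say.** If the within-arm correlation is ρ, the numerator becomes ρ + dx·dy/4. An opposite-signed ρ can cancel the arm part; at 0.8/0.8 this happens at ρ = −0.16. So arm effects on both variables do not force a non-zero pooled slope.

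**H1B2.** The table models one pair of change scores per person. H1B2 uses repeated runs, including a baseline run before any feedback (Section 4.5.2), when arm can have had no effect. The mechanism carries over through H1A and H1B1; the percentages do not.

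**The case against.** Several points on the other side have force.

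- **Status.** Aim 1C is labelled exploratory, and H1C2 and H1B2 are worded as correlations. A reader might infer that these regressions are the trial's proof that brain change drives benefit. The documents do not say so. This stands and limits the weight of the point, although Aim 1B carries no exploratory label.
- **Mediation.** The mechanistic question also goes to a mediation analysis that includes NF group, and a conventional model would condition the PFC-to-outcome path on group. But the equations are not stated, it is not the named test of H1C2, and it does not cover H1B2. It helps only in part.
- **Meaning of the hypothesis.** H1C2 concerns activation induced by feedback. The randomised part of that is the between-arm difference, which a group term removes; the within-arm slope rests on non-randomised variation and can itself be confounded. This is a good reason to keep the pooled slope. It does not make that slope informative about linkage, since the between-arm differences are already tested under H1A and H1C1.
- **Narrow scenario.** A large false-positive rate needs sizeable arm effects on both variables with none of the outcome effect tracking PFC change. Blinding (Section 4.3.2) and a sham signal matched on success rate (Section 4.3.4) are meant to limit such routes. They reduce the risk but cannot exclude it.
- **Baseline scores.** A reader might infer that baseline HAM-A and ERQ go unused. They enter the H1C2 change scores and the H1C1 mixed models. Replacing the change score with a baseline-adjusted follow-up score would be a preference, not a correction.
- **Arm 1.** A reader might infer that the unblinded arm 1 is in the analysis set. Every group factor in Section 6 has only the levels veritable-NF and sham-NF, so the randomised arms are the natural reading. A clarifying sentence is all that is needed.

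**Conclusion.** The point holds as a modest, inexpensive improvement. The H1C2 and H1B2 regressions omit a variable that the plan expects to affect both sides, so a pooled association would partly restate the arm comparison. For H1C2 the effect is slight when both arm effects are about 0.5 SD or less (rejection of about 5% to 7% at N=40 to 60) and material when both are large (18-19% at 0.8/0.8 and 24-25% at 1.0/0.8, N=60). All these figures rest on assumed N and effect sizes, equal allocation and zero within-arm association. No rate is claimed for H1B2.

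The stronger reading, that success on H1A and H1C1 guarantees confirmation of H1C2, is not supported. The induced correlations are small, most simulated trials in the tabulated settings still do not reject, and an opposite within-arm association can cancel the arm component.

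**What to change.** In Section 6:

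1. Add group (veritable-NF, sham-NF) as a covariate in the H1C2 regressions, and group with its interaction with run in the H1B2 models.
2. Report the arm-adjusted slope beside the pooled one, and base any statement that PFC change tracks benefit on the arm-adjusted slope.
3. Write out the mediation equations, with group in the outcome model.
4. State that the analysis set for these regressions is randomised arms 2 and 3.

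This is a change of wording and needs no new data. It costs one degree of freedom for H1C2 and a few for H1B2. The adjusted slope also loses some power if the effect is carried wholly by the between-arm difference, which is why the pooled slope should stay in the report.
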